4.5.2. Adverse Events

AEs will be coded during the course of the trial according to the Medical Dictionary for Regulatory Activities (MedDRA, version 25.0 or later). AEs will be presented by primary system organ class (SOC) and preferred term (PT).

Treatment-emergent AEs will be summarised; however, all AEs recorded during the course of the trial will be included in subject data listings. An event will be considered treatment-emergent if it started after the first IMP administration or if it started before the first IMP administration and worsened in severity after the first IMP administration. The tabulations described in the following will only include the treatment-emergent AEs. In each of the tabulations, AEs are defined by MedDRA PTs within primary SOC.

Unless otherwise specified, AEs will be summarised in terms of the number of subjects with at least 1 event, the percentage of subjects with at least 1 event, the number of events and the event rate per 100 patient years of exposure, and the tables will only include treatment-emergent AEs reported in the treatment period.

Event rate = (number of events/patient years) × 100.

Related AEs are defined as AEs for which the investigator has not described the causal relationship to the IMP as 'not related'.

An overall summary will be presented for subjects with any treatment-emergent AEs in the following categories:

- Any treatment-emergent AEs
- AEs leading to Deaths
- Serious adverse events (SAEs); Non-Serious adverse events
- AEs leading to permanent discontinuation from IMP
- AEs leading to withdrawals from the trial
- Treatment-related AEs
- Severe AEs
- Outcome of AEs
- Action taken with IMP

The overall summary table will also be provided for:

- All treatment-emergent AEs reported in treatment period and the safety follow-up period. Event rate will be per 100 patient years of observation.

Patient years of observation (years) = (date of end of study – date of first IMP administration + 1)/365.25.

- Treatment-emergent AEs reported in safety follow-up period. Event rate will be per 100 patient years of safety follow-up.

Patient years of safety follow-up (years) = (date of end of study – date of last IMP administration)/365.25.

- Lesional/Perilesional Treatment-emergent AEs reported in treatment period. Event rate will be per 100 patient years of exposure.
- Serious Treatment-emergent AEs reported in treatment period. Event rate will be per 100 patient years of exposure.
- Treatment-emergent AEs leading to withdrawals from the trial reported in treatment period. Event rate will be per 100 patient years of exposure.

Tabulations by SOC and PT will be presented for treatment-emergent AEs started in the treatment period for the following categories:

- All AEs
- Related AEs
- AEs by severity
- AEs by causal relationship to IMP
- Most frequent AEs ($\geq 5\%$ in any treatment group)
- Lesional/Perilesional AEs
- SAEs
- AEs leading to withdrawal from trial
- AEs leading to permanent discontinuation of IMP

Tabulations by SOC and PT will also be provided for treatment-emergent AEs started in treatment period and the safety follow-up period (event rate based on 100 patient years of observation) and treatment-emergent AEs started in the safety follow-up period (event rate based on 100 patient years of safety follow-up).

In the summary of AEs by severity, if an AE worsens in severity, the severity will be reported as the most severe recording for that AE. In the summary of causal relationship to IMP, subjects will be counted only once in the most related category (e.g. probably related). If the severity or relationship is missing, the AE will be counted as “severe” or “probably related”. The number of missing severity/relationship will be stated in the footnote of summary tables, and the listing will display the actual missing severity/relationship.

The following by-subject listings will be provided:

- All AEs
- SAEs
- AEs leading to withdrawal from trial
- AEs leading to permanent discontinuation of IMP
- AEs occurred after the first overdose of IMP

The detailed listing will provide an overview of the individual cases and include the age and sex of the subject, treatment received at the time of AE onset, the AE preferred and reported terms,

causality and severity of the AE, the action taken with the IMP, AE outcome, start and stop date of AE, duration of AE and number of days since first and last IMP administration. No narratives will be given except for SAEs and pregnancies.

Other events involving IMP (medication error, misuse and abuse of IMP) will be tabulated by treatment. Event rate will be calculated based on 100 patient years of exposure. Other events involving IMP will also be listed. No narratives will be given.

4.5.3. Additional Safety Assessments

4.5.3.1. Clinical Laboratory Evaluation

For laboratory parameters, the absolute values as well as the changes from baseline will be summarised by visit for each treatment group.

A shift table will be produced for chemistry parameters showing the categories (“Low”, “Normal”, “High” according to the normal range) at baseline against those at each post-baseline visit.

For subjects with post-baseline values, out of reference range events reported up to end of study will be summarised.

A by-subject listing will be provided for laboratory data.

4.5.3.2. Physical Examination and Other Observations Related to Safety

For physical examination, abnormalities at baseline and end-of-treatment (or early termination) as well as the transition from baseline to end-of-treatment (or early termination) will be summarised for each treatment group.

A by-subject listing will be provided for physical examination data.

Urine and Serum pregnancy test performed, reasons why not performed, and test results (“positive”, “negative”) will be listed.

4.6. Other Analyses

4.6.1. Other Variables and/or Parameters

4.6.1.1. Health Economics

Health economics parameters are not evaluated in this trial.

4.6.1.2. CCI

The analysis on CCI are described in Section 4.4.

4.6.2. Subgroup Analyses

Subgroup analysis is not planned in this trial.

4.6.3. Pharmacokinetics, Pharmacokinetic-Pharmacodynamic Relationships

Pharmacokinetic or pharmacodynamic parameters are not evaluated in this trial.

4.7. Interim Analysis

No interim analysis is planned during the trial.

4.8. Changes to Protocol-planned Analyses

Baseline PGA is added as a covariate to the ANCOVA model for continuous endpoints, which is not mentioned as a covariate in Protocol section 9.3.5.3.

The MedDRA search term in Protocol section 9.3.9.1 will not be applied to AE summary.

For subjects with post-baseline values, out of reference range events reported up to end of study will be summarised, instead of up to week 6 in Protocol section 9.3.9.3.

5. Sample Size Determination

Data from the EU SmPC is used for the sample size calculation[4]. Table 5–1 shows results from a historical comparative trial on the “Percentage of subjects with 'treatment success' according to the PGA of the body at Week 4 (PGA 0/1)”. These data from the SmPC give a relative risk of 1.27 and a crude OR of 1.59 in favour of LEO 90100.

Table 5–1 EU SmPC Trial Result

Data from SmPC	LEO 90100	Daivobet® ointment
Trial Three	(N=141) 54.6%	(N=135) 43.0%

Abbreviations: SmPC=Summary of Product Characteristics.

Table 5–2 illustrates the power with 600 subjects randomised 1:1. The probability of superiority and non-inferiority is found by running 10,000 simulations using the data from the EU SmPC. The responder probabilities are used in a binomial sampling of the number of subjects with treatment success. For each of the simulations, the OR with 95% CI limits is calculated using Fisher's exact test and the lower 95% boundary is used to evaluate superiority and non-inferiority at the thresholds 1 and **CCI** respectively.

Table 5–2 Simulated Power

Endpoint	Proportion responders for Daivobet® ointment	Proportion responders for LEO 90100	Probability of superiority	Probability of non-inferiority with a NI margin OR=CCI	Probability of point estimate for LEO 90100 exceeds Daivobet® ointment (OR > 1)
PGA 0/1 at Day 29	43.0%	54.6%	0.799	0.9198	0.9975

Abbreviations: NI=non-inferiority; OR=odds ratio; PGA=Physician's Global Assessment of disease severity.

6. Supporting Documentation

6.1. Appendix 1: List of Abbreviations

Abbreviation / Acronym	Definition / Expansion
AE	Adverse event
ANCOVA	Analysis of Covariance
BMI	Body Mass Index
CCI	CCI [REDACTED]
CI	Confidence interval
CSP	Clinical Study Protocol
eCRF	electronic Case Report Form
DBL	Database Lock
CCI	CCI [REDACTED]
EDC	Electronic Data Collection
FAS	Full Analysis Set
FCS	Fully Conditional Specification
ICF	Informed consent form
ICH	International Council for Harmonisation
IE	Intercurrent Event
IMP	Investigational Medicinal Product
IWRS	Interactive Web Response System
LS	least square
MAR	Missing at random
MedDRA	Medical Dictionary for Regulatory Activities
(m)PASI	(modified) Psoriasis Area and Severity Index
NRI	Non-Responder Imputation
OR	Odds Ratio
PGA	Physician's Global Assessment of disease severity
CCI	CCI [REDACTED]
CCI	CCI [REDACTED]
PT	Preferred Term
CCI	CCI [REDACTED]
SAE	Serious adverse event
SAP	Statistical Analysis Plan
SD	Standard Deviation
CCI	CCI [REDACTED]
SmPC	Summary of Product Characteristics
SoA	Schedule of Activities
SOC	System Organ Class
TEAE	Treatment-emergent adverse event
TFLs	Tables, Figures and Listings
WHO	World Health Organization

6.2. Appendix 2: Supporting Study Information

6.2.1. Disposition of Subjects

A clear accounting of the disposition of all subjects who enter the study will be provided based upon all screened subjects, from screening to study completion.

The number of subjects in the following categories will be summarized based on the all screened set:

- Subjects screened (i.e. signed informed consent)
- Subjects passed screening
- Subjects failed screening
 - The criteria not satisfied
- Subjects met all eligibility but discontinued before randomisation

Disposition of subjects for treatment completion and study completion will be summarized by treatment group and overall. The number and percentage of subjects in the following categories will be summarized based on all randomised subjects.

- Subjects randomised
- Subjects randomised but not treated
- Subjects treated (with at least one dose of IMP)
- Subjects included in Full Analysis Set
- Subjects included in Safety Analysis Set
- Subjects completed treatment
- Subjects permanently discontinued IMP (including reasons of IMP discontinuation)
- Subjects completed study
- Subjects discontinued from study (including reasons of study discontinuation)

A summary of the number and percentage of subjects in each analysis set (FAS, safety analysis set) will be provided. Percentage will be based on all randomised subjects.

The following by-subject listings will be provided:

- Subjects disposition with their screening and withdrawal/study completion details (including reason for discontinuation) (all screened set)
- Subjects randomisation assignment with stratification factors (all randomised subjects)
- Subjects analysis set assignment (all randomised subjects)

6.2.2. Demographics

Descriptive statistics of demographics will be presented for all randomised subjects by treatment group.

- Age (years)
- Age categories (\leq 35 years, 36-50 years, 51-64 years, \geq 65 years)
- Sex (Male, Female)
- Is child-bearing potential (Yes, No)
- Race (Chinese)

A by-subject listing of demographic for all randomised subjects will be provided.

6.2.3. Baseline and Disease Characteristics

Descriptive statistics of baseline and disease characteristics will be presented for all randomised subjects by treatment group.

- Height (cm)
- Weight (kg)
- Body mass index (BMI) (kg/m^2)
- Fitzpatrick skin type
- Psoriasis history
 - Years of having psoriasis
 - Type of psoriasis
 - Location
- Previous anti-psoriatic treatment
 - Any previous anti-psoriatic therapy (Yes, No)
 - Treatment type
 - Medication
 - Systemic therapy and topical medications will be coded by World Health Organization (WHO) Drug Global Dictionary, version Sep 2022 or later. ATC Level 2, ATC Level 4 and PT will be summarised.

A summary of baseline values of efficacy variables will be presented for all randomised subjects by treatment group.

- PGA
- mPASI
- CCI [REDACTED]
- CCI [REDACTED]
- CCI [REDACTED]
- CCI [REDACTED]

A by-subject listing of baseline and disease characteristics for all randomised subjects will be provided.

6.2.4. Treatment Compliance

Treatment compliance will be calculated based on the duration and frequency of IMP administration:

Treatment compliance (%) = (Days with once IMP administered/duration of exposure to IMP) ×100,

Duration of exposure to IMP = date of last IMP administration – date of first IMP administration + 1.

Treatment compliance during the total treatment period will be presented for each treatment group for the safety analysis set.

A by-subject listing on treatment compliance will be provided.

6.2.5. Protocol Deviations

Protocol deviations will be handled in accordance with Parexel Standard Operating Procedures (SOPs).

Major protocol deviations are defined as those deviations from the protocol likely to have an impact on the perceived efficacy and/or safety of study treatments.

Decisions to exclude subjects from the will be made before DBL in a blinded manner. A by-subject listing of major protocol deviations will be provided. A summary of the number and percentage of subjects with a major protocol deviation by type of deviation will be provided based on all screened subjects. PDs due to COVID-19 will be listed separately.

6.2.6. Medical History and Concurrent Illnesses

Medical history will be coded using Medical Dictionary for Regulatory Activities (MedDRA) version 25.0 or later.

Medical history events will be summarized for randomised subjects by preferred term (PT) and system organ class (SOC) by treatment group and overall as:

- Past medical history if confirmed not to be ongoing at screening.
- Current medical history if confirmed to be ongoing at screening.

Past and current medical history will be listed separately.

6.2.7. Prior/Concomitant Medications and Procedures

Medication and/or procedure start and stop dates will be compared to the date of first IMP administration to be classified as below:

- Prior only: medications/procedures that start and stop prior to the date of first IMP administration.
- Both prior and concomitant: medications/procedures start before the date of first IMP administration and stop on or after the date of first IMP administration.
- Concomitant only: medications/procedures start on or after the date of first IMP administration.

Medications/procedures start after the completion/withdrawal date will be listed but will not be classified or summarized.

Medications will be coded using World Health Organization (WHO) Drug Global Dictionary, version Sep 2022 or later. The following medications will be summarized by Anatomical Therapeutic Chemical (ATC) code (levels 2 and 4) and PT for all randomised subjects. In case of missing level 4 coding the level 3 coding will be used.

- Prior medications
- Concomitant medications (including both prior and concomitant medications and concomitant medications)
- Rescue medications (concomitant medications indicated as rescue treatment)

Procedures will be coded using MedDRA Version 25.0 or later. Concomitant procedures will be summarized by SOC and PT for all randomised subjects.

By-subject listings will be provided for all medications and procedures with the flag of classifications for all randomised subjects.

6.3. Appendix 3: Data Handling Conventions

6.3.1. Analysis Visit Windows

6.3.1.1. Effectiveness

Visit windows are defined in Schedule of Assessments (SoA) ([Appendix 4](#)).

No visit window re-mapping will be performed. The analysis will be based on the nominal visit collected in EDC.

6.3.1.2. Safety

Visit windows are defined in Schedule of Assessments (SoA) ([Appendix 4](#)).

No visit window re-mapping will be performed. The analysis will be based on the nominal visit collected in EDC.

6.3.2. Missing Date Imputation

6.3.2.1. Missing/Incomplete AE Start Date

For analyses of AEs, a complete date must be established in order to correctly identify the AE as occurring during treatment or not. For purposes of imputing missing components of partially reported or missing start and stop dates for AEs, the algorithms listed below will be followed. Start and stop dates of AEs in the subject data listings will be displayed as reported (i.e., no imputed values will be displayed in data listings).

Partial or missing AE start dates will be imputed as follows:

Imputation of partial or missing start dates:

- If only the month and year are specified and the month and year of first dose is not the same as the month and year of the start date, then use the 1st of the month.
- If only the month and year are specified and the month and year of first dose is the same as the month and year of the start date, then use the date of first dose.
- If only the year is specified, and the year of first dose is not the same as the year of the start date, then use the 1st of January of the year of the start date.
- If only the year is specified, and the year of first dose is the same as the year of the start date, then use the date of first dose.

- If the start date is completely unknown and the stop date is unknown or not prior to the date of first dose, then use the date of first dose.
- If the start date is completely unknown and the stop date is prior to the date of first dose of IMP, then set the start date to the 1st of January of the year of the stop date.

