8.4.1 Time Period and Frequency for Collecting AE and SAE Information

All AEs and SAEs will be collected from the signing of informed consent form (ICF) until the end-of-trial (defined as attending the last visit in the trial [the early termination visit or the last follow-up visit (Visit 5), whichever comes last]), at the timepoints specified in the SoA ([Table 1–1](#)).

It will be recorded in the eCRF if the AE started prior to first IMP administration.

All SAEs will be recorded and reported to LEO Pharma A/S immediately without undue delay but no later than within 24 hours of awareness, as indicated in [Appendix 3](#). The investigator will submit any updated SAE data to LEO Pharma A/S within 24 hours of it being available.

Investigators are not obliged to actively seek information on AEs or SAEs after the conclusion of trial participation. However, if the investigator learns of any SAE, including a death, at any time after a subject has been discharged from the trial, and the investigator considers the event to be reasonably related to the IMP or trial participation, the investigator must promptly notify LEO Pharma A/S.

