10.3.3 Recording and Follow-up of AE and SAE

AE and SAE Recording

AEs must be assessed by a physician.

When an AE/SAE occurs, it is the responsibility of the investigator to review all documentation (e.g., hospital progress notes, laboratory and diagnostics reports) related to the event.

AEs reported by the subject or observed by the investigator must be recorded on the AE form of the eCRF and should be described in the following manner:

The AE term must be in precise English medical terminology (that is, not necessarily the exact words used by the subject). Whenever possible, a specific diagnosis should be stated (e.g., 'allergic contact dermatitis').

For cutaneous AEs, the location must be part of the AE description and may be described as (e.g., the face, scalp, back, chest, arm, leg, trunk or limb). Additionally, the location should be described using the following terminology:

- Lesional/perilesional (≤ 2 cm from the border of lesion [s] treated with the IMP).
- Distant (> 2 cm from the border of lesions [s] treatment with the IMP).

The duration of the AE must be reported by the start date and stop date of the event, unless the event is ongoing. If the event is ongoing, it will be marked as ongoing. In addition, it will be recorded if the AE started prior to first IMP administration.

AEs must be classified in terms of severity, causality and outcome according to the definitions provided below.

Action taken with IMP: Any action taken with IMP as a consequence of the AE must be recorded (dose not changed, drug withdrawn, not applicable, unknown).

Withdrawal from trial due to this AE: It must be recorded whether the AE led to withdrawal from the trial.

Other action taken: Any other action taken as a result of the AE must be recorded (none, concomitant medication, concurrent procedure).

Assessment of Intensity

The severity of the AE should be described in terms of mild, moderate or severe according to the investigator's clinical judgement. If the AE worsens in severity, the new severity including date of worsening, should be recorded. However, if an AE with onset prior to IMP initiation worsens after IMP administration, a new AE should be recorded:

- **Mild:** An AE that is usually transient and may require only minimal treatment or therapeutic intervention. The event does not generally interfere with usual activities of daily living.

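### The AE start-date rule can date an event's start after its recorded stop, because it checks neither the stop date nor the pre-dose flag

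*SAP*

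**What the plan says.** SAP 6.3.2.1 gives the purpose of the imputation: "a complete date must be established in order to correctly identify the AE as occurring during treatment or not". Its rules for the start date fall into three pairs.

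- **Month and year known.** If they differ from those of first dose, the first of the month is used. If the dosing month "is the same as the month and year of the start date, then use the date of first dose".
- **Year only known.** If the years differ, 1 January is used. If "the year of first dose is the same as the year of the start date, then use the date of first dose".
- **Start completely unknown.** Only here is the stop date consulted. "If the start date is completely unknown and the stop date is prior to the date of first dose of IMP", the start becomes 1 January of the stop year. Otherwise it becomes the first-dose date.

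The same section says that "no imputed values will be displayed in data listings".

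Protocol 8.4.1 adds a data item for AEs: "It will be recorded in the eCRF if the AE started prior to first IMP administration". Protocol 10.3.3 repeats it ("it will be recorded if the AE started prior to first IMP administration") and requires a stop date unless the event is ongoing. SAP 4.5.2 then classifies: "An event will be considered treatment-emergent if it started after the first IMP administration". An event that started earlier but worsened in severity after first dose also counts.

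**The concern.** AEs are collected from consent, and screening can last up to 4 weeks, so the database can hold events that began, and even ended, before dosing. When such an event has a partial start date in the month or year of first dose, the rule replaces it with the first-dose date even where the stop date or the flag already shows that onset was earlier. The section therefore fails its own stated purpose in cases where the trial has recorded the answer.

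Treatment-emergent status feeds the AE tabulations in SAP 4.5.2 and the secondary safety endpoint, the number of TEAEs per subject from baseline to Day 43. If the first-dose date counts as on treatment, pre-treatment events would be added to those counts. Because listings show dates as reported, a reader could find an event listed as ending before first dose but counted as treatment-emergent in the tables.

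**Working it through.** The documents give no figure to reproduce. The check applies the rules literally.

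**1. One event, three levels of date information.** Illustrative inputs: first dose 25 March, AE stop 10 March, flag showing onset before first IMP.

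| Start date as recorded | Imputed start | Against stop date |
|---|---|---|
| Month and year (March) | 25 March | 25 − 10 = 15 days after the AE ended |
| Year only | 25 March | 15 days after the AE ended |
| Completely unknown | 1 January of that year | before the stop and before dosing |

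The record with the least date information is placed correctly, and the two with more are not.

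**2. How often the rule bites, among partially dated screening AEs only.** Assumptions: first dose equally likely on each of 365 days, and true onset 1 to 28 days earlier, each equally likely. That gives 365 × 28 = 10,220 combinations.

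- Month and year known: the onset escapes the default only if it falls in an earlier month than first dose. Each month contributes 28 + 27 + … + 1 = 406 such combinations, so 12 × 406 = 4,872. Share moved to the first-dose date: 1 − 4,872/10,220 = 52%.
- Year only: the onset escapes only across a year boundary, 406 combinations. Share moved: 1 − 406/10,220 = 96%.

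Now also let the AE stop on any day from onset to the day before dosing. There are 365 × 406 = 148,190 combinations. The imputed start falls after the recorded stop in 38% of them (month and year known) or 95% (year only).

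These are shares of partially dated screening AEs under uniform dates. They are not expected counts.

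**3. Direction.** For true onsets 0 to 42 days after first dose (365 × 43 = 15,695 combinations), neither partial-date rule ever gave a start before first dose. Relative to the first-dose date, the error runs one way: pre-dose onsets are moved forward to it.

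**4. From imputed date to TEAE status.** The imputed date equals the first-dose date, while SAP 4.5.2 speaks of a start after first administration. Two readings are possible.

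- The first-dose date counts as on treatment: the screening events above are wrongly classed as treatment-emergent.
- Strictly after: those events stay out, but on-treatment AEs with a start imputed to the first-dose date drop out too.

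The stated purpose of the rule points to the first reading. The SAP does not say so.

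**5. Comparison within the SAP.** The next subsection, 6.3.2.2 on medication dates, does use evidence that a medication started or stopped before IMP. The AE rule lacks the equivalent check.

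**The case against.** Defaulting to first dose is a common, conservative safety convention when nothing else is known, since it errs towards counting an event. That stands; the fault is only that the default overrides recorded evidence. The trigger should also be uncommon. Start and stop dates must be reported, subjects are asked about AEs at every visit, dates can be queried, and subjects needing no washout go straight to Day 1. A year-only start for an event less than four weeks old is hard to picture. That stands too.

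A reader might infer more than the documents support:

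- **That screening AEs definitely become on-treatment events.** This depends on how the first-dose date is classed, which SAP 4.5.2 does not settle.
- **That the SAP excludes the flag.** It is silent. Nothing forbids using it, and the TEAE definition turns on the same fact that the flag records.
- **That events dated Day 1 cannot be classified.** With the flag they can be, and an event with a full Day 1 date is outside 6.3.2.1.
- **That any difference between foam and ointment is diluted.** Screening precedes randomisation, so the added event rate c should be similar in both arms. Then (a + c) − (b + c) = a − b: the expected rate difference is unchanged, and only a ratio moves towards 1. The planned TEAE summaries are descriptive and outside the testing hierarchy.
- **That negative AE durations will appear.** Duration is mentioned only for the listing, listings show dates as reported, and nothing says that duration is computed from imputed dates.

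**Conclusion.** The rule is wrong as written, and the consequence is minor. Followed literally, it can date an AE's start after its recorded end, although the stop date and the pre-dose flag are both collected. This follows from the text and needs no assumption about frequency.

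The effect on results is conditional. If a start on the first-dose date counts as treatment-emergent, some pre-treatment events are wrongly counted in the descriptive TEAE tables and in the secondary safety endpoint. The documents do not give the number of partially dated AEs. It is probably small, and the misplacement should be similar in the two arms. Efficacy, the confirmatory tests, alpha and power are untouched.

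**What to change.** In SAP 6.3.2.1, put a condition ahead of the list. The first-dose default applies only when the stop date is missing or on/after first dose, and the eCRF flag does not say that the AE started before first IMP. Otherwise, class the AE as not treatment-emergent (unless it worsened after first dose) and impute a start that fits the known date parts and is no later than the stop date. Do not force that start before the day of consent: screening and first dose can fall on the same day, so a cap at the day before dosing would be wrong. One choice that works is the later of the consent date and the first day of the known month or year.

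In SAP 4.5.2, state that an AE dated or imputed to the first-dose date is treatment-emergent unless the flag says that it started before first IMP.

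The cost is a few sentences of SAP text and one programming condition on fields already collected. No new data are needed.
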